#### 7.4.2 Futility monitoring

In general, for futility assessment, destroying all the CD8s in the tumor and all the HPV-specific response in the blood would argue that we are likely preventing an immune response with the current CRT treatment, thus making the addition of pembrolizumab ineffective. Clinical response to pembrolizumab is most commonly associated with CD8+ T cell infiltration into tumors, and response rates for other solid malignancies are approximately 20% with pembrolizumab as a monotherapy. Thus, if CRT causes a reduction in the number of patients with T cell infiltration we could anticipate that CRT reduces the likelihood of patients responding to treatment. Assuming the current study population has a similar potential to respond to pembrolizumab, we would deem the study futile if early evidence indicates a potential to respond in a much lower percentage of subjects. We have set this lower target to be 5%. Futility will be monitored separately for each arm.

For each subject, the potential to respond will be determined at the end of the 12 week treatment window. We will assess the subject's tumor and blood for the presence of immune infiltrate and HPV specific T cell responses. Futility will be assessed by monitoring the number of patients with the absence of both CD8+ T cells and NK cells in the tumor, and a concomitant loss of HPV T cell reactivity in the blood. For the assessment of futility, each subject will be deemed to have the potential to respond if there are CD8+ T cells or NK cells in the tumor, or no loss of HPV T cell

Protocol/Amendment No.: UVA-LACC-PD201, Version 4.0, 06 March 2018

reactivity in the blood. A 3-stage design structure will be used to monitor for a null potential to respond of 5% versus and alternative rate of 20%.

Within an arm, the futility assessments will occur after accrual of 14, 29 and 44 subjects have been accrued and followed for 12 weeks. The study specific arm will be deemed futile if 0/14, <4/29 or <6/44 subjects have the potential to respond for assessment at stages 1, 2 or 3, respectively. The decision guideline has type I and II error rates of 0.015 and 0.185, respectively.

#### 7.5 Analyses

The study is designed with sufficient power to assess pre/post change in immune measures with an ES of .45 within each arm and not to detect a predetermined difference in the changes overtime between the two arms. However, data from the study will be used to estimate; the magnitude of the difference in pre/post change for all parameters of interest between the two arms; as well as progression—free and overall survival. With 44 eligible patients per arm we have 67%, 75% and 87% power to detect an ES of 0.45, 0.5 and 0.6, respectively, for continuous immune parameters (normality assumed) with a 10% level t-test. With 44 patients the width of a 90% CI (exact Clopper-Pearson) around the complete metabolic response at 3 months of 70% and the distant metastases rate at 3 years of 20% are (57%, 81%) and (10%, 33%), respectively. Thus, any estimated rate outside of these bounds would be considered promising. For each arm, progression free survival (PFS) and overall survival will be estimated by the product-limit method of Kaplan and Meier along with 90% confidence bands. In patients with complete metabolic response at 3 months, 3-year PFS is 78% (Schwartz et al, 2007). This result will be used to guide interpretation of results on PFS from this study.

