#### 7.1.3 Efficacy Endpoints

All eligible patients for which a PET/CT imaging is obtained 12 weeks after CRT will be evaluated for complete metabolic response.

All eligible patients with follow-up information on disease status will be evaluated for the occurrence of distant metastasis as the first site of recurrence, progression-free survival and overall survival.

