## 7.4 Safety and Futility Monitoring

## 7.4.1 Safety monitoring

Dose Limiting Toxicity (DLT) is defined as an adverse event which: i) is determined to be at least possibly related to treatment with pembrolizumab; ii) occurs within the first 30 days after the first pembrolizumab infusion; and iii) meets one of the below criteria:

- Pneumonitis Grade  $\geq$  3
- Any non-hematological toxicity Grade  $\geq$  3, except for the following:
  - Grade 3 toxicity that is expected from standard of care cisplatin and radiation
  - Grade 3 Colitis, hypophisitis, or hyperthyroidism lasting less than 7 days
  - Grade 3 electrolyte toxicities that are corrected to grade 1 or less within 24 hours
  - Grade 3 hypertension that can be controlled with oral medications and does not require treatment delay for > 7 days
  - Grade 3 diarrhea that is not refractory to anti diarrhea medications and is corrected to Grade 1 or less within 48 hours
  - Grade 3 nausea and vomiting that is not refractory to anti-emetic therapy and is corrected to Grade 1 or less within 48 hours
  - Grade 3 rise in creatinine, if corrected to Grade 2 or less after up to 2 liters of intravenous fluids within 24 hours
  - Grade 3 elevation in AST/ALT if < 1.5 times the baseline level
  - Grade 3 elevation of ALP (alkaline phosphatase)
  - Grade 3 hypoalbuminemia
  - o Grade 3 lymphopenia

- Grade 3 rash if it returns to ≤ grade 2 after 1 week of symptomatic treatment
- Any Grade ≥ 4 toxicity
- Other AEs if they are clearly related to pembrolizumab and are causing substantial morbidity for subjects, as determined by the study chair.

Within each arm, safety will be assessed by monitoring the number of patients who experience a DLT. Results reported in ASCO 2015 abstracts [22, 23] for pembrolizumab in combination with other treatments resulted in an overall DLT rate of 1/59=2% with a 90%Cl(1%, 8%). For this study the upper boundary of a sequential probability ratio test (SPRT) based upon a binomial test of proportions for DLT will be used for monitoring to protect against excessive failure rates. The stopping boundary is for a SPRT contrasting a 5% versus 25% DLT rate, with nominal type I and II errors of 10% and 10%, respectively. The slope of the parallel line for monitoring is 1.190 and the intercept is 0.128.

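### Section 7.5's 90% interval of (10%, 33%) for a 20% distant-metastasis rate in 44 patients is not the exact one: the lower limit, which serves as the favourable cut-off, should read 11%.

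*Combined protocol and SAP*

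**What the plan says.** Section 7.5 describes the precision expected in each arm. It begins "With 44 patients the width of a 90% CI (exact Clopper-Pearson) around the complete metabolic response at 3 months of 70" per cent and ends "the distant metastases rate at 3 years of 20% are (57%, 81%) and (10%, 33%), respectively". The method (exact Clopper-Pearson), the level (90%), the denominator (44) and the two rates (70% and 20%) are therefore all given.

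The sentence that follows puts the intervals to use: "Thus, any estimated rate outside of these bounds would be considered promising".

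Section 7.1.3 sets the denominator for distant metastasis: "All eligible patients with follow-up information on disease status will be evaluated" for distant metastasis as first site of recurrence. Section 7.2 plans for 44 eligible patients per arm and raises total accrual to 98 to allow for 10% ineligibility or drop-out. Section 3.2 lists the distant-metastasis rate among the secondary objectives.

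**The concern.** An interval printed with its method, level, rate and denominator should reproduce, and this one does not. A small slip in a descriptive interval would normally be trivial. Here the limits are also the yardstick for calling a result promising. For an endpoint where fewer events are better, the lower limit is the bar a good result has to get under, and a bar printed too low makes a borderline good result read as unremarkable. What is at stake is the label on a secondary endpoint.

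**Working it through.** **Inputs (Section 7.5).** n = 44; level 90%, so 5% in each tail; rates 70% and 20%.

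**Formula.** For x events in n, the lower limit is the 0.05 quantile of Beta(x, n − x + 1) and the upper limit is the 0.95 quantile of Beta(x + 1, n − x).

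**Step 1: the companion interval.** 70% of 44 is 30.8. With x = 30.8 the limits are 56.7% and 81.2%, which round to the printed (57%, 81%). Using 31/44 gives 57.2% and 81.6%, or (57%, 82%). The printed pair therefore points to the fractional count with ordinary rounding.

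**Step 2: the distant-metastasis interval.** 20% of 44 is 8.8.

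| Count | Exact 90% limits | Rounded |
|---|---|---|
| 8/44 | 9.4%, 30.4% | (9%, 30%) |
| 8.8/44 | 10.8%, 32.5% (32.47%) | (11%, 32%) |
| 9/44 | 11.1%, 33.0% | (11%, 33%) |
| Printed | | (10%, 33%) |

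No row rounds to the printed pair. As a tail check for 9/44, the chance of 9 or more events is 0.050 at a true rate of 11.1% but 0.028 at 10%, so 10% lies below the exact limit.

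**Step 3: is it a rounding convention?** Rounding 8.8/44 outward would give (10%, 33%). Rounding the companion outward would give (56%, 82%), which is not what is printed. One convention does not yield both pairs. Wilson, Wald, Agresti-Coull, Jeffreys, mid-P, logit and Blaker intervals, and 80% or 95% exact limits, do not give (10%, 33%) at n = 44 either.

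**Step 4: effect with 44 evaluable.** 4/44 = 9.1% and 5/44 = 11.4%. A lower bound of 10%, 10.8% or 11.1% leaves 4 or fewer events as the favourable result. At the upper end 14/44 = 31.8% and 15/44 = 34.1%, so no count falls between 32% and 33%.

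**Step 5: effect with more than 44 evaluable.** Accrual of 98 is 98/2 = 49 per arm. The lower limit is recomputed for 20% of each n:

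| n | 5 events | Exact lower limit | Against 10% | Against exact limit |
|---|---|---|---|---|
| 45 | 11.11% | 10.85% | inside | inside |
| 46 | 10.87% | 10.94% | inside | outside |
| 47 | 10.64% | 11.03% | inside | outside |
| 48 | 10.42% | 11.11% | inside | outside |
| 49 | 10.20% | 11.19% | inside | outside |

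These limits use the fractional count, as in Step 1. If x is instead the nearest whole count, the lower limits are 10.60% (9/46), 10.37% (9/47), 11.76% (10/48) and 11.51% (10/49), and only n = 48 and 49 change side.

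**Step 6: non-crude estimates.** Section 7.5 names Kaplan-Meier for progression-free and overall survival but no estimator for the 3-year distant-metastasis rate. A time-to-event estimate is not tied to whole counts and could fall between 10% and about 11%.

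**The case against.** The strongest reply is that nothing changes at the planned size. The interval is stated for 44 patients, and at 44 the count rule is the same under either bound. That stands. Having 46 to 49 evaluable means losing 3 or fewer of 49 (3/49 = 6.1%), which is better than the plan's own 10% allowance. That also stands: those cases are possible but not the planning case. The time-to-event case rests on an estimator the plan does not name. And the promising label is an interpretive remark in a study that, by Section 7.0, seeks preliminary estimates and not definitive comparisons. None of this makes the printed interval correct.

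A reader might infer three stronger things that the documents do not support.

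- **That smaller denominators, such as 37 to 39, also change the reading.** They appear to only if the 44-patient bound is carried over. Recomputed at the actual n, the lower limits are 10.03%, 10.14% and 10.25%, while 4 events give 10.81%, 10.53% and 10.26%: still inside, with n = 39 a tie to rounding. At n = 40 the limit is 10.36% and 4/40 is exactly 10.0%, so that case turns on whether a rate equal to the printed bound counts as outside. For 39 to 41 patients, (10%, 33%) is in fact the correctly rounded interval for 20%.
- **That the 90% interval of (1%, 8%) for 1/59 in Section 7.4.1 is also an error.** The exact limits are 0.09% and 7.8%, so the 1% lower limit is not the exact value. But Section 7.4.1 names no method, the 8% is right, and a flat-prior Bayesian interval (0.60%, 7.66%) rounds to (1%, 8%). The stopping boundary is built on 5% versus 25% and does not use this interval.
- **That the slip affects trial decisions.** No sample-size, safety or futility rule uses these bounds.

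**Conclusion.** The point holds as a minor numerical correction. Under the plan's stated method, level, rate and denominator, the lower limit is 10.8% (20% of 44) or 11.1% (9/44), not 10%, so the favourable cut-off is 0.8 to 1.1 points too low. The printed upper limit of 33% is right for 9/44 and about half a point high for 8.8/44.

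The practical effect is nil for a crude rate in exactly 44 patients. It is confined to 5 events among 46 to 49 evaluable patients (48 or 49 only under nearest-whole counts) or to a non-crude estimate between 10% and about 11%.

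Two assumptions underlie this. The lower limit is taken as the favourable side, although the plan's sentence gives no direction. The fractional count is taken as the intended convention because it reproduces the companion interval.

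**What to change.** In Section 7.5, replace (10%, 33%) with (11%, 32%), or with (11%, 33%) if 9/44 is the intended count. Add one sentence saying that the bound will be computed from the actual evaluable number in each arm at analysis, and by which count convention. Optionally, name the interval method in Section 7.4.1 or give the lower limit for 1/59 as 0.1%; the stopping boundary stays as it is. The cost is one figure and one sentence, with no new data and no change to the design.

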## 7.2 Sample size and accrual

Results in Jordanova ES, et al 2008, report estimates of CD8+/Treg for normal cervix and cervical cancers tissue for cervical cancer patients who underwent radical hysterectomy with lymphadenectomy.[4] These data provide the assumed "natural baseline" of cancer patients' in this study with CD8+/Tregs being lower in cancer tissue, and results in a Cohen's *d*av effect size (ES) of 0.45. Estimated sample size is based upon being able to detect a similar effect size between CD8+/Tregs at baseline and end of CRT, and baseline to the 12 weeks post CRT assessment without correction for multiple comparisons. Data from Nilges, K et al, 2003, indicates a mean (standard deviation) of 23.32 (15.39) in CD8+/Tregs measured in the tumor infiltrating lymphocytes (TIL) from patients with cervical cancer. Given these data, 44 eligible patients are required (per arm) to assess change in pre/post CD8+/Tregs with an ES of 0.45 with type I and II errors of 10%. Each within arm comparison supports the following hypothesis. Cisplatin can kill T cells, therefore the CRT may eliminate both CD8+ HPV CTL and Tregs, and the ensuing or concurrent pembrolizumab treatment may increase the CD8+/Treg ratio (test that pembrolizumab will increase CD8+/Tregs to an ES of 0.45).

Adjusting for an overall 10% ineligibility/drop-out rate, maximum accrual to the study is estimated at 98 patients. Accrual is estimated at 4 patients a month, thus accrual to the study should be completed by 2.0 years with primary analysis at 3 years.

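### Section 7.5 names neither a data cut nor a censoring-aware estimator for the 3-year distant-metastasis rate, so a crude proportion read against the 'promising' bound could be biased low

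*Combined protocol and SAP*

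**What the plan says.** Distant metastasis as first site of recurrence is a secondary objective (section 3.2, item 2), listed there without a time point. Section 7.5 supplies the time point, "the distant metastases rate at 3 years of 20" per cent, and the only method shown for it. The sentence begins "With 44 patients the width of a 90% CI (exact Clopper-Pearson) around the complete metabolic response at 3 months of 70" per cent, goes on to the metastasis rate, and gives intervals that "are (57%, 81%) and (10%, 33%), respectively". It is followed by the reading rule that "any estimated rate outside of these bounds would be considered promising". Later in the same paragraph, "progression free survival (PFS) and overall survival will be estimated by the product-limit method of Kaplan and Meier along with 90% confidence bands"; distant metastasis is not included.

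Section 7.1.3 defines who is counted: "All eligible patients with follow-up information on disease status will be evaluated for the occurrence of distant metastasis as the first site of recurrence". It requires no minimum length of follow-up.

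The one calendar time given for an analysis is in section 7.2: "accrual to the study should be completed by 2.0 years with primary analysis at 3 years". Section 1.0 ties that date to the primary endpoint. Sections 5.7.1 and 6.3.5.4 follow subjects for 5 years. No section says when the distant-metastasis rate will be estimated, or how to treat a patient whose follow-up ends before 3 years.

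**The concern.** A rate at 3 years is a time-to-event quantity. A binomial interval with all 44 patients in the denominator is right only if each patient's status at 3 years is known. If some are censored earlier and still counted, each is scored as metastasis-free, and the estimate can only move down. For this endpoint down is the favourable direction, and the lower bound of 10% is where a result would be called promising. (The rule gives no direction; I take below 10% as the intended favourable side.)

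The same paragraph uses a censoring-aware method for PFS and OS, so the omission is a gap specific to this endpoint. What is at stake is a false favourable signal on a secondary endpoint that may inform later work.

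**Working it through.** **Inputs from the documents.** 44 patients per arm, a 3-year rate of 20%, a 90% exact interval and a lower bound of 10% (section 7.5); 2.0 years of accrual with primary analysis at 3 years (section 7.2). At "Accrual is estimated at 4 patients a month", 98 patients take 98/4 = 24.5 months, consistent with 2 years.

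**Inputs assumed.** The documents give no event timing, so I assume uniform accrual over 2 years and, as base case, a constant hazard with a true 3-year rate of 20%. Competing events are left out of the calculation.

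**1. The plan's interval.** Clopper-Pearson at 90% with n = 44:
- x = 8.8 (exactly 20%) gives (10.8%, 32.5%), and x = 9 gives (11.1%, 33.0%). The stated (10%, 33%) is reproduced to within about 1 point.
- x = 30.8 (70%) gives (56.7%, 81.2%), matching (57%, 81%).

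The printed interval is therefore a plain binomial one on 44 fully observed patients.

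**2. Complete 3-year follow-up.** A rate below 10% means 4 or fewer of 44 (4/44 = 9.1%; 5/44 = 11.4%). P(X ≤ 4) for Binomial(44, 0.20) = 0.044.

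**3. Crude proportion at the year-3 primary analysis.** Follow-up is then uniform on 1 to 3 years. With λ = −ln(0.8)/3 = 0.0744, the expected crude proportion is

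1 − (e^(−λ) − e^(−3λ))/(2λ) = 1 − (0.9283 − 0.8000)/0.1488 = 0.137.

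P(X ≤ 4) for Binomial(44, 0.137) = 0.26.

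**4. Other assumed event timings at the same cut, true rate still 20%.**

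| Timing | Mean crude rate | P(below 10%) |
|---|---|---|
| Weibull shape 0.6 | 15.9% | 0.15 |
| Constant hazard | 13.7% | 0.26 |
| Weibull shape 1.2 | 12.8% | 0.32 |
| 50% of 3-year events in year 1 | 15.0% | 0.19 |
| 80% of 3-year events in year 1 | 18.0% | 0.08 |

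**5. Censoring-adjusted estimate at the same cut.** In a simulation of 20,000 trials (constant hazard, no competing events), Kaplan-Meier at year 3 averages 19.6% and falls below 10% with probability 0.14. Only 4 to 5 of 44 patients are still at risk at 2.75 years. The adjustment removes almost all the bias but not the imprecision of an early cut.

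**6. Later cuts, crude proportion, constant hazard.** At year 4 it averages 18.5%; at year 5, when every patient has 3 years of potential follow-up, 20.0%.

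**7. Losses to follow-up at the mature cut.** With a loss hazard μ = −ln(1 − annual loss), the expected crude rate is λ/(λ + μ) × (1 − e^(−3(λ + μ))).
- 5% a year: μ = 0.0513; 0.0744/0.1257 × (1 − e^(−0.377)) = 18.6%.
- 10% a year: μ = 0.1054; 0.0744/0.1797 × (1 − e^(−0.539)) = 17.2%.

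Both loss rates are illustrative; the documents give no figure for yearly loss.

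**The case against.** The strongest reply is that the plan never schedules this endpoint at the year-3 analysis. That date belongs to the primary endpoint, which is immunologic and safety-related, and 5 years of follow-up lets every patient reach 3 years. A reader might infer from sections 7.2 and 7.5 together that the reported rate will be biased low. The documents do not support that as a statement of fact: the bias of step 3 depends on a cut that is neither stated nor ruled out. This part of the objection stands.

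A reader might also infer that competing events would still distort the crude rate after mature follow-up. They would not. With everyone observed to 3 years, patients who die or recur locally first stay in the denominator as non-events under both the crude proportion and the Aalen-Johansen estimate, and the two coincide.

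Third, comparing 26% with 4.4% mixes bias with immaturity. At the same cut a proper estimator still gives about 14%, so a large part of the rise comes from cutting early. That also stands, and it is why the choice of cut matters as much as the estimator.

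Fourth, the Clopper-Pearson sentence is worded as a statement of precision, not expressly as the final estimator, and section 7.0 disclaims definitive comparisons between the arms. No stopping or go/no-go rule hangs on the word promising. This limits the consequence. It does not close the gap: no other method is given for the rate, the reading rule is applied to it, and section 7.1.3 admits patients with any follow-up.

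**Conclusion.** The point holds as a gap in specification with a one-sided consequence. Followed as written, the plan allows a crude proportion in which patients censored before 3 years count as metastasis-free, read against a bound that favours low values.

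Its size depends on the unstated cut. At year 3 a true 20% would average about 13.7% (13% to 18%), with a 26% chance (8% to 32%) of falling below 10%; the fair comparators are 4.4% with complete follow-up and about 14% with a censoring-adjusted estimate at that cut. At a cut where all have 3 years of potential follow-up, the administrative-censoring bias disappears and only losses matter, taking the rate to 18.6% or 17.2% under the assumed losses. Losses are plausible: section 6.3.5.4 relies on yearly telephone contact with no specified assessments, and section 5.7.2 ends all follow-up on withdrawal of consent.

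All these figures rest on assumed uniform accrual, assumed event timing and no competing events. The endpoint is secondary and descriptive, so the correction is worth making but does not threaten the primary analysis.

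**What to change.** In section 7.5, state that the 3-year rate of distant metastasis as first recurrence will be estimated in each arm by cumulative incidence (Aalen-Johansen) with a 90% CI. Death and non-distant first recurrence are competing events, and patients without an event are censored at their last disease assessment. Name the data cut, and apply the bound for a promising result only once all patients have 3 years of potential follow-up. Both parts are needed, because the estimator alone does not rescue an early cut (step 5).

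The cost is a few sentences and one standard analysis, with no change to design, visits or sample size. The price is a slightly wider interval than the binomial one and a later reading of this secondary endpoint.

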#### 3.2 Secondary Objectives

- To estimate rates of complete metabolic response on PET/CT imaging obtained 12 weeks after CRT.
- (2) To estimate rates of distant metastasis as the first site of recurrence for patients.
- (3) To estimate the influence of concurrent and consolidative MK-3475 on levels of plasminogen activator inhibitor-1 (PAI-1), a marker of immunosuppressive TGF-B.
- (4) To estimate the influence of concurrent and consolidative MK-3475 on levels of IDO, an enzyme that depletes tryptophan, which is essential for T-cell function.
- (5) To estimate the influence of concurrent and consolidative MK-3475 on levels of MHC class I (CD8+ T cell ligand) and MICA (NK ligand), as measured by MHC.
- (6) To estimate the progression free survival (PFS) in subjects with locally advanced cervical cancer treated with sequential and concurrent administration of pembrolizumab in relation to CRT.
- (7) To estimate the overall survival (OS) in subjects with locally advanced cervical cancer treated with sequential and concurrent administration of pembrolizumab in relation to CRT.

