## 4.3 Rationale

## 4.3.1 Rationale for the Trial and Selected Subject Population

We hypothesize that CRT in LACC will be beneficial to the immunostimulatory activity of pembrolizumab compared to single agent use. This hypothesis is based on evidence that platinumbased DNA intercalators and irradiation are highly effective at inducing a form of apoptosis known as immunological cell death (ICD),[8] which can lead to auto-vaccination that is promoted by blocking checkpoint molecules such as PD-1. We anticipate that ICD will not only curtail the immunosuppressive activity of T cells, but will also increase the source of antigen and improve the context of antigen presentation (by activating dendritic cells) that could lead to greater immune cell activation in the cervical cancer environment. However, cisplatin is deleterious to activated effector T cells (our unpublished data), and irradiation and chemotherapy can recruit myeloid cells and regulatory cells with immunosuppressive function.[9, 10] Therefore, the sequencing of SOC with PD-1 blockade deserves considerable attention, with the intent of defining optimal treatment regimens and the development of prognostic and predictive biomarkers. These observations suggest that PD-1 blockade is a potential therapeutic strategy to increase immune responses against cervical cancer. Pembrolizumab (MK-3475) is an PD-1 antibody approved for use in melanoma,[11] and the proposed study focuses on evaluating the influence of the addition of pembrolizumab to standard CRT, and sequencing of pembrolizumab with CRT, on CD8+ infiltrating T cells in subjects with locally advanced cervical cancer.

Secondary objectives of the study will estimate clinical endpoints to obtain preliminary data regarding the potential clinical effect of the combination. We will estimate the rate of complete metabolic response as measured by PET/CT at 12 weeks, as well as the rate of distant (versus local) recurrence.

There is no data available to predict the optimal time point to incorporate immunotherapy into a treatment course. Therefore, this study will evaluate biological endpoints and responses to immunotherapy given at the time of chemotherapy and following completion of chemotherapy.

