## 7.0 STATISTICAL CONSIDERATIONS

This is a randomized phase II study to assess the safety of CRT in combination with pembrolizumab given as consolidation therapy or current with CRT, and to obtain preliminary estimates of the immunologic effect of the addition of pembrolizumab to CRT in this patient population. Eligible participants will be randomized 1:1 between the two arms. All participants receiving any protocol treatment will be evaluated for safety and the primary immunologic endpoint which is the ratio of the phenotype of HPV-specific CD8+ T cells to regulatory T cells (CD8+/Treg). Patterns of change in other immunologic endpoints assessed in the tissue and blood will be estimated along with 90% confidence intervals. The purpose is not to make definitive comparisons between arms but to obtain preliminary estimates of change in CD8+ T-cells and regulatory T cells over time for the different treatment schedules.

Arm 1: pembrolizumab after completion of CRT Arm 2: pembrolizumab concurrent to CRT

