Safety stopping guidelines for the occurrence of DLTs are detailed in the following table. If a stopping bound is crossed in either arm then accrual to the study will be suspended until the study PI, co-investigators and the DSMC can review the data, and determine if the study should continue, be amended or be closed to further accrual.

Incidence of treatment related DLTs	
Number of patients in an Arm	Stopping boundary
2-6	≥ 2
7-14	≥ 3
15-21	≥ 4
22-29	≥ 5
30-37	≥ 6
38-44	≥ 7

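### The criterion for a promising complete metabolic response or distant metastasis rate names no side, so an unfavourable result meets it

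*Combined protocol and SAP*

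**What the plan says.** Section 7.5 (Analyses) takes 44 patients per arm and gives exact Clopper-Pearson 90% intervals around two reference rates: complete metabolic response of 70% at 3 months and distant metastasis of 20% at 3 years. The intervals are printed together: "distant metastases rate at 3 years of 20% are (57%, 81%) and (10%, 33%), respectively". One sentence then interprets both: "Thus, any estimated rate outside of these bounds would be considered promising".

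No other section gives a direction. Section 3.2 lists the endpoints for estimation only: "To estimate rates of complete metabolic response on PET/CT imaging obtained 12 weeks after CRT" and "To estimate rates of distant metastasis as the first site of recurrence for patients". Section 4.3.1 describes their purpose: "Secondary objectives of the study will estimate clinical endpoints to obtain preliminary data regarding the potential clinical effect of the combination". Section 7.1.3 says which patients will be evaluated for each and sets no threshold.

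**The concern.** The two endpoints point in opposite directions: more complete responses are better, more distant metastases are worse. No single phrase without a direction can be right for both. As worded, the sentence takes in all four tails, two of which are unfavourable: a response rate below 57% and a metastasis rate above 33%.

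This is the only stated criterion for reading either rate. It is meant to say when the preliminary clinical signal is encouraging, and followed exactly it gives that label to results worse than the plan's own reference values.

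The other count-based rules in Section 7 do state their side. The dose-limiting toxicity table in Section 7.4.1, introduced by "Safety stopping guidelines for the occurrence of DLTs are detailed in the following table", uses at-or-above counts, from 2 or more among 2 to 6 patients up to 7 or more among 38 to 44. The rule in Section 7.4.2 uses below-threshold counts: "The study specific arm will be deemed futile if 0/14, <4/29 or <6/44 subjects have the potential to respond".

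**Working it through.** **Inputs (Section 7.5).** n = 44 per arm; two-sided 90% exact intervals; reference rates 70% (response) and 20% (metastasis); printed bounds (57%, 81%) and (10%, 33%). Assumptions: all 44 patients are evaluable, and the 3-year metastasis rate is a simple proportion without censoring, as the plan's own interval treats it. True rates other than 70% and 20% are illustrative.

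**Step 1: reproduce the intervals.** Lower limit = 5% quantile of Beta(x, n − x + 1); upper limit = 95% quantile of Beta(x + 1, n − x).

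- Response, x = 0.70 × 44 = 30.8: (56.7%, 81.2%), which rounds to the printed (57%, 81%).
- Metastasis, x = 0.20 × 44 = 8.8: (10.8%, 32.5%), against the printed (10%, 33%). The nearest whole counts give (9.4%, 30.4%) for x = 8 and (11.1%, 33.0%) for x = 9.

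Both intervals reproduce to within about one percentage point.

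**Step 2: turn the bounds into counts.**

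- Response, low side: 25/44 = 56.8%. This is below the printed 57% but above the unrounded 56.7%, so the cutoff is 25 or fewer (printed) or 24 or fewer (unrounded).
- Response, high side: 36/44 = 81.8%, so 36 or more with either bound.
- Metastasis, low side: 4/44 = 9.1% and 5/44 = 11.4%, so 4 or fewer with either bound.
- Metastasis, high side: 14/44 = 31.8% and 15/44 = 34.1%, so 15 or more with either bound.

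**Step 3: chance of landing on each side.** Exact binomial sums, X ~ Bin(44, p).

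| True response rate | Low side, X ≤ 25 (printed) | Low side, X ≤ 24 (unrounded) | High side, X ≥ 36 |
|---|---|---|---|
| 50% | 85.4% | 77.4% | 0.0% |
| 60% | 38.7% | 27.7% | 0.2% |
| 70% (plan) | 4.4% | 2.2% | 5.6% |
| 80% | 0.0% | 0.0% | 47.0% |

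| True metastasis rate | High side, X ≥ 15 | Low side, X ≤ 4 |
|---|---|---|
| 10% | 0.0% | 54.7% |
| 20% (plan) | 2.0% | 4.4% |
| 30% | 32.8% | 0.1% |
| 40% | 83.0% | 0.0% |

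**Step 4: effect of naming the side.** At the plan's reference rates, the literal rule gives the label with probability 4.4% + 5.6% = 10.0% for response (2.2% + 5.6% = 7.8% with the unrounded bound) and 2.0% + 4.4% = 6.4% for metastasis. With only the favourable side, these fall to 5.6% and 4.4%. At favourable true rates almost nothing changes: 47% at an 80% response rate and 55% at a 10% metastasis rate, with or without a direction.

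**The case against.** The strongest reply is that nobody would misread the sentence. To call a result promising means it favours the treatment; Section 7.5 goes on to use progression-free survival in complete metabolic responders as a reference, so it treats response as the good outcome; and distant metastasis can only be bad. On that view the 85% and 83% describe a misreading and not a risk to the trial. Nothing acts on the label either: both rates are secondary, Section 7.0 says of the trial "The purpose is not to make definitive comparisons between arms", and sample size, toxicity stopping and futility do not use it. The toxicity and futility rules trigger action and so need an operator; a remark about interpretation arguably does not.

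Most of this stands, and it limits the weight of the point. The intended side can be inferred, and the probabilities in the unfavourable tails apply only if the sentence is followed as written. What it does not remove is that a prespecified criterion, the only one for these rates, yields the wrong answer when applied exactly.

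A smaller reply concerns the printed 10% bound. It gives the same cutoff as the computed 10.8% at 44 patients, but Section 7.1.3 restricts these analyses to patients with the scan or with follow-up. With 38, 39 or 40 evaluable, 4 events (10.5%, 10.3%, 10.0%) would be below 10.8% but not below 10%. That is correct, and the fix should say which figure governs.

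**Conclusion.** The point holds and is minor. It is an error of wording in a stated criterion, not a flaw in the design or the estimation. Literally applied at 44 evaluable patients per arm, the sentence calls 25 or fewer responses (24 or fewer with the unrounded bound) or 15 or more metastases promising. For the illustrative worse true rates examined, the unfavourable tail meets the criterion 39% (60%) to 85% (50%) of the time for response with the printed bound, or 28% to 77% with the unrounded bound, and 33% (30%) to 83% (40%) of the time for metastasis. At the plan's own reference rates the excess is small: 10.0% or 7.8% against 5.6%, and 6.4% against 4.4%. Sample size, the primary analysis and the stopping rules are unaffected.

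**What to change.** Replace the sentence in Section 7.5 with wording such as: *For each arm, an estimated complete metabolic response rate above 81%, or an estimated 3-year distant metastasis rate below 10%, will be called promising. A rate inside the bounds, or beyond the opposite bound, will not.*

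The last part makes explicit something the plan leaves unsaid, so the sponsor should confirm it. The printed 10% can stay: at 44 patients it gives the same cutoff as the computed 10.8% (4 or fewer). If fewer are evaluable, the printed figures should be stated to govern.

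The cost is one sentence. It needs no new data and no change to sample size, endpoints or denominators.
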